#### 2.1.2.10.2.7 Changes from baseline in the inflammatory marker (CRP) and cytokines to each time point.

(1) Analysis set : FAS

(2) Analysis item : changes from baseline in the inflammatory marker (CRP) and cytokines (each time point - Day 1)

(3) Time point : Day 1, Day 3, Day 5, at discontinuation/completion of treatment

(4) Analytical method :

- 1) Summary statistics (number of patients, arithmetic mean, standard deviation, median, minimum, maximum) for measured values and changes from baseline in inflammatory marker (CRP), cytokine markers (measured values and log2 log-transformed values of IL-6, IL-1 $\beta$ , TNF- $\alpha$ , IL-10, CCL17, CXCL9, MMP-12) and CXCL9/CCL17 ratios to each time point will be calculated by treatment group and by time point. In addition, a chart for the mean  $\pm$  standard deviation over time will be prepared by treatment group.
- 2) Estimated values of differences between groups, 95% confidence intervals and the p-values (Day 3, Day 5, at discontinuation/completion of treatment) will be calculated using mixed effect model for repeated measures with and changes from baseline in inflammatory marker (CRP) and cytokine markers (measured values and log2 log-transformed values of IL-6, IL-1 $\beta$ , TNF- $\alpha$ , IL-10, CCL17, CXCL9, MMP-12) and CXCL9/CCL17 ratio to each time point as response variables, baseline values as the covariate, time point, treatment group, and time point \* treatment group as the fixed

effects. In addition, a chart for the changes in estimated values and 95% confidence intervals over time will be prepared by treatment group.

2.1.2.10.2.8 Distribution and proportion of patients in each category on a 7-point ordinal scale from Day 0 until Day 28

(1) Analysis set : FAS

(2) Analysis item : 7-point ordinal scale

(3) Time point : Day 0 to Day 28

(4) Analytical method :

1) The number of patients and the proportion in each category on the 7-point ordinal scale shown in Table 2.1 from Day 0 until Day 28 will be summarize by treatment group and by time point (number of patients, %). In addition, a bar chart showing the percentage of each category will be prepared by treatment group and by time point.

2) For patients who were categorized in each category on a 7-point ordinal scale on Day 14 (or at the last observation the point) and Day 28 (or at the last observation time point between Day 15 and Day 27), the p-values (Wilcoxon's rank sum test) of the differences between groups will be calculated.

2.1.2.10.2.9 Distribution and proportion of patients in each category of oxygen requirement until Day14

(1) Analysis set : FAS

(2) Analysis item : oxygen requirement

(3) Time point : Day 0 to Day 14

(4) Analytical method :

1) The number of patients and the proportion in each category on the oxygen requirement shown in Table 2.2 until Day 14 will be summarize by treatment group and by time point (number of patients, %). In addition, a bar chart showing the percentage of each category will be prepared by treatment group and by time point.

2) For patients who were categorized in each category on the oxygen requirement on Day 5 and Day 14, the p-values (Wilcoxon's rank sum test) of the differences between groups will be calculated.

Table 2.2 Oxygen requirement

Category	Ordinal scale
1	Require oxygen supply of 4 L/min or more using oxygen mask
2	Require oxygen supply of 2 L/min or more using nasal cannulas
3	Require oxygen supply of less than 2 L/min using nasal cannulas
4	Do not require oxygen supply but feel shortness of breath during walking or moving
5	Do not require oxygen supply and do not feel shortness of breath during walking or moving

Table 2.3 Definition of event/censoring in Time to event analysis

Analysis item	Event/ Censoring	Definition of event/censoring	Period

 
Period to the first improvement by at least 2-rank between baseline and Day 28 on a 7-point ordinal scale 
 
Period from baseline to the day of discharge
 
Period from baseline to shifting to Category 6 or 7 on a 7-point ordinal scale
 
Period from baseline to shifting to Category 5 on a 7-point ordinal scale
 
Period to from baseline to improvement by 1 rank or more on a 7-point ordinal scale
 
 
 
	Event	A patient who developed an event	Period until the onset of the first event
	Censoring	A patient who completed the study without any event	Period until the last observation day
		A patient who discontinued or died	Censored after complementing 29 days*
Period from baseline to shifting to Category 1 or 2 (worsening) on a 7-point ordinal scale	Event	A patient who developed an event	Period from baseline to shifting to Category 1 or 2 (worsening) on a 7-point ordinal scale
	Censoring	A patient who completed the study without any event	Period until the last observation day
		A patient who discontinued or discharged from the hospital	Period until discontinuation or discharge

\*Reasons for setting: In the event of early discontinuation due to worsening, the improvement rate may be overestimated due to the drop out of the patient who developed the event from the denominator. This was set in order to conservatively assess the improvement rate.

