2 Observation and Examination Schedule

Item	Screening	Date of allocation	Observation period ⁵⁾												Discontinuation/ Exit Test ⁶⁾
			Day 0	Day 1	Day 2	Day 3	Day 4	Day 5	Day 6	Day 7	Day 8	Day 9	Day 10	Day 11 ~14	Day 15 ~28
Acceptable window	To Day 0	-2 days ⁷⁾	—	—	—	—	—	+1 day ⁷⁾	—	—	—	—	—	—	+1 day
Informed consent	●														
Medical history/current medical conditions	●														
Subject characteristics	●														
Height and weight	●														
Inclusion and exclusion criteria	●														
Percutaneous oxygen saturation (SpO2)	●														
Allocation		●													
Study drug administration ¹⁾			●	●	●	●	●	●	○	○	○	○	○		
7-point ordinal scale ²⁾			●	●	●	●	●	●	●	●	●	●	●	●	
Oxygen requirement			●	●	●	●	●	●	●	●	●	●	●	●	
Arterial blood gas analysis (PaO2, PaCO2, A-aDO2, others)			● ³⁾					●							●
Inflammatory markers, cytokines			● ³⁾		●		●								●
Chest HRCT or plain chest CT or Chest X-ray			●					●							●
Physical examination			●					●							●
Vital sign			●					●							●
12-lead ECG			●					●							●
Laboratory tests (blood chemistry, hematology and urinalysis)			●					●							●
Pregnancy test (urine or blood sample)			●												
adverse events ⁴⁾				●									●		
Concomitant medication/therapy		●	—									●			

● : Will be performed in all the subjects ○ : Will be performed only in the subjects who continue to receive the study drug after Day 5.

1) Inhalation administration will be started on the morning of Day 1 and performed twice daily (morning, evening) for 5 days, in principle (up to 10 days).

2) Will be evaluated every day during the period between Day 1 and Day 28. Use or no use of a ventilator will be included in this evaluation.

3) Will be performed prior to study drug administration.

4) Only the adverse events that have occurred until Day 14 after the start of study drug administration. may be collected and entered in the electronic case report form. Serious adverse events related to the study drug administration will be collected until Day 28.

- 5) Assessment of efficacy on the 7-point ordinal scale and oxygen requirement will be performed after completion of the second dose (inhalation) of the day.
- 6) Will be performed on the day of discontinuation if study drug administration has been prematurely discontinued before Day 5, or on the day of the last dose in the case that the last day is not Day 5.
- 7) Except 7-point ordinal scale and oxygen requirement.

3 Study Administrative Structure

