Considering the mechanism of action of sargramostim, patients with clinically diagnosed pneumonia whose respiratory function is suggestively decreased are to be included in the study. In addition, patient population without use of invasive ventilator yet (the category of a patient that falls into one of Category 3 to 5 on a 7-point ordinal scale (see Table 13.3-1)) is to be chosen in order that an accurate dose of study drug can be administered by inhalation.

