13.12 Oxygen requirement

The investigators will evaluate the category of oxygen requirement of a subject classified in 5 categories, referring to Table 13.12-1. The date of evaluation and the results will be entered in the eCRF.

Table 13.12-1 Oxygen Requirement

Category	Ordinal scale
1	Require oxygen supply of 4 L/min or more using oxygen mask
2	Require oxygen supply of 2 L/min or more using nasal cannulas
3	Require oxygen supply of less than 2 L/min using nasal cannulas
4	Do not require oxygen supply but feel shortness of breath during walking or moving
5	Do not require oxygen supply and do not feel shortness of breath during walking or moving.

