15.2 Withdrawal of a subject from the study

A subject who meets any of the following criteria shall be withdrawn from study participation.

- (1) The subject was found not to meet the inclusion criteria or to meet the exclusion criteria and to be ineligible for the clinical study according to the results of medical examinations, etc. performed after start of the clinical study.
- (2) The subject or the legally acceptable representative has requested to terminate the clinical study or to withdraw his/her consent.
- (3) The subject was dead.
- (4) The investigators judged that continuation of the clinical study is not desirable for the subject due to other reasons.

[Rationale]

- (1) It was set as a general item to ensure safety of the subject and to properly evaluate the study.
- (2) It was set in accordance with the principles of the Declaration of Helsinki and the GCP.
- (3) Since continuous observation cannot be performed, it was set as a discontinuation criterion due to inevitable accident.
- (4) In addition to above mentioned criteria, it was set as a general item for discontinuation criteria so that the investigators can judge appropriateness to continue the clinical study.

If an event occurs to meet the criteria for withdrawal of subjects from the study, the investigators shall follow the following procedures.

- The date of discontinuation (the date on which discontinuation was judged and the date of last dose, if possible) and the reason for discontinuation, as well as comments on discontinuation if necessary, will be entered in the eCRF.

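### The oxygen-requirement rank tests leave out patients who have died, and the Day-28 ordinal-scale test can lose deaths by Day 14; the SAP should rank death explicitly

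*SAP*

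**What the plan says.** **7-point scale (SAP 2.1.2.10.2.8, method 2).** Arms are compared by Wilcoxon rank-sum test at two time points, each with its own fallback. The first is "on Day 14 (or at the last observation the point"), with no lower limit on how far back the last observation may lie. The second is "Day 28 (or at the last observation time point between Day 15 and Day 27"), which starts at Day 15. Category 1 of the scale is death.

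**Oxygen requirement (SAP 2.1.2.10.2.9, method 2).** The Wilcoxon tests are run "For patients who were categorized in each category on the oxygen requirement on Day 5 and Day 14", with no fallback. Table 2.2 has five categories. The worst is "Require oxygen supply of 4 L/min or more using oxygen mask", and none is for death.

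**Recording after death.** Note 2 to the protocol's Observation and Examination Schedule says of the 7-point scale: "Will be evaluated every day during the period between Day 1 and Day 28". Protocol 15.2(3) makes death a reason for withdrawal: "Since continuous observation cannot be performed, it was set as a discontinuation criterion due to inevitable accident". Neither document says that Category 1 is carried forward.

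**General rules (SAP 2.1.2.14).** Item (3) sends otherwise unspecified missing data to the Case Review Committee before data fixation. Item (4) sets up a missing category for summaries, but only up to completion or discontinuation. Neither assigns a rank. Table 2.3 has a rule for death, for the time-to-event analyses only.

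**The concern.** In a rank test on a severity scale, a death should be the worst outcome. If it is removed, the test compares survivors, and an arm with more early deaths is not penalised for them. The resulting p-value does not reflect an early-mortality difference in either direction, benefit or harm.

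The two tests of the 7-point scale can also treat the same death differently. A patient who dies on Day 10, with Category 1 recorded that day, enters the Day-14 test as Category 1 through the open fallback. The same patient is absent from the Day-28 test unless someone enters Category 1 again.

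The SAP was the place for such a rule, because protocol 5.2.1.8 and 5.2.1.9 leave the details of the categories to it. The footnote to Table 2.3 shows that the sponsor saw the related risk in the time-to-event analyses, where losing patients who worsen could flatter the improvement rate. The rank tests have no counterpart.

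**Working it through.** **1. Which deaths are kept, applying the text literally**

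| Test | Death before the test day | Basis |
|---|---|---|
| 7-point, Day 14 | Kept if Category 1 was recorded at death | Open fallback |
| 7-point, Day 28, death on Days 15-27 | Kept if Category 1 was recorded at death | Inside fallback window |
| 7-point, Day 28, death by Day 14 | Kept only if Category 1 is entered again on Day 15 or later | Before the window; no carry-forward rule |
| Oxygen, Day 5 and Day 14 | Left out | No category for death; categorized patients only |

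**2. Inputs.** The plan states no power or effect size for these tests, so there is no figure to reproduce. Its only power figure, 82.1% in protocol section 18, belongs to the primary log-rank test and does not bear on this point. Taken from the documents: 40 active and 20 control patients, Wilcoxon rank-sum, two-sided 5%. Assumed, because the documents give no mortality: the death rates and the distributions among survivors, which are identical in both arms throughout.

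**3. Exact effect on the Mann-Whitney probability.** Let pa and pc be the proportions dead in the active and control arms. With deaths ranked worst, the probability that an active patient does better than a control patient, ties counting half, is

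(1 - pa)(1 - pc)/2 + (1 - pa)pc + pa·pc/2 = 0.5 + (pc - pa)/2,

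whatever the survivor distribution. With deaths dropped it is 0.5.

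- 2% vs 5%: 0.5 + 0.03/2 = 0.515
- 5% vs 10%: 0.5 + 0.05/2 = 0.525
- 5% vs 15%: 0.5 + 0.10/2 = 0.55

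Expected deaths among 60 patients are 40 × 0.02 + 20 × 0.05 = 1.8 at 2% vs 5%, and 40 × 0.05 + 20 × 0.15 = 5.0 at 5% vs 15%.

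**4. Day-28 test, simulated rejection rates.** Normal approximation with tie correction, 100,000 trials per scenario (Monte Carlo standard error at most 0.5/√100,000, or 0.16 points). Survivor pattern A: 8% Category 4, 92% Category 7. Pattern B: Categories 2 to 7 at 3/4/8/10/5/70%. Cells show deaths ranked worst / deaths dropped.

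| Death by Day 14, active vs control | Pattern A | Pattern B |
|---|---|---|
| 0% vs 0% | 3.8% / 3.8% | 4.9% / 4.9% |
| 2% vs 5% | 6.5% / 3.6% | 6.0% / 5.0% |
| 5% vs 10% | 8.8% / 3.7% | 7.0% / 4.9% |
| 5% vs 15% | 18.0% / 4.0% | 12.2% / 5.0% |
| 5% vs 25% | 46.7% / 3.9% | 31.5% / 4.9% |
| 15% vs 5% | 12.1% / 3.5% | 9.7% / 4.9% |

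With balanced deaths of 5% vs 5%, a separate run (8,000 trials; survivors 80% Category 7, 5% Category 6, 5% Category 5, 7% Category 4, 3% Category 2) gave about 4% either way.

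**5. Oxygen tests, same method.** Four distributions of living patients over Categories 1 to 5: 10/15/20/25/30%, 20% each, 5/10/15/20/50%, and 30/25/20/15/10%. Death is by the day of the test. Ranges are over the four.

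| Death, active vs control | Ranked below Category 1 | Dropped |
|---|---|---|
| 2% vs 5% | 5.5-5.7% | 4.9-5.1% |
| 5% vs 10% | 6.4-6.6% | 4.8-5.0% |
| 5% vs 15% | 10.4-10.9% | 4.8-4.9% |

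With deaths dropped, rejection stays at or just below 5% whatever the mortality difference.

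**The case against.** **The Day-28 gap may be closed in practice.** Category 1 describes a state, as Category 7 (discharged) does, and the scale is rated daily to Day 28. If death counted only on its own day, the planned Day-28 distribution would hardly show it. Entering Category 1 needs no further observation of the patient. This stands as a likely reading: the plan does not instruct anyone to exclude early deaths from the Day-28 test, and a reader who infers that goes too far. But nothing requires the entry once the patient has been withdrawn.

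**The Case Review Committee can settle it.** The committee acts before data fixation, and protocol 10.5 has the data locked blinded, so a choice made with knowledge of allocation is not the planned route. That limits bias, but it is still no prespecified rank.

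**The oxygen scale measures oxygen need, not survival.** An analysis of living patients is a legitimate, narrower question, and ranking death makes the test a composite. This is a fair cost. The plan does not, however, say that the test is meant for survivors only.

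**Living patients on advanced support.** Table 2.2 also names no category for noninvasive ventilation, high-flow oxygen, invasive ventilation or ECMO, although eligible patients include those for whom "the category of a patient that falls into one of Category 3 to 5 on a 7-point ordinal scale", and Category 3 covers the first two. A reader might infer that these patients are left out too. The documents do not support that. Protocol 13.12 says "The investigators will evaluate the category of oxygen requirement of a subject classified in 5 categories", so each living patient has to be given one of the five, presumably Category 1. Stating this would be an optional clarification.

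**Little depends on these tests.** They are secondary and unpowered, and SAP 2.1.2.13 makes no multiplicity adjustment. This stands, and it sets the severity.

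**Conclusion.** The point holds as a minor one, limited to death. The oxygen-requirement tests as written always omit patients who have died. The Day-28 test omits deaths by Day 14 if Category 1 is not entered again after withdrawal.

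The size depends on early mortality, which the documents do not give. It is negligible if early deaths are few or balanced. Under the assumed 5% vs 15%, the Day-28 rejection rate falls from 12-18% to 4-5% and the oxygen rate from about 10-11% to 5%. The loss is larger only with greater imbalance.

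Two stronger conclusions are not supported. First, a chosen split of deaths can produce a striking change in p-value, but such figures depend on the survivor pattern: 1 of 40 against 4 of 20 deaths, ranked, gives 0.10 under pattern A and 0.22 under pattern B. None is evidence of the effect in this trial. Second, the trial's mortality signal is not hidden. The primary analysis has its own rule for death in Table 2.3. Death or invasive support to Day 28 is tested in SAP 2.1.2.10.2.4, and deaths are listed under SAP 2.1.2.11.1.3. The Day-14 ordinal test can also retain early deaths. What is affected is how the Day-28 ordinal and the oxygen-requirement p-values are read.

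**What to change.** Add two statements to the SAP before the allocation code is released under protocol 10.5:

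- **SAP 2.1.2.10.2.8:** a patient who has died is Category 1 at every later time point through Day 28 and enters the Day-28 test as such. The Day-14 fallback can stay as it is.
- **SAP 2.1.2.10.2.9:** in the Day-5 and Day-14 tests, patients who have died by that day are ranked below Category 1. A survivors-only version may be shown as a sensitivity analysis.

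The cost is a few sentences and a derivation from the 7-point score already collected daily, with no new assessments. The downside is that the oxygen test becomes a composite of oxygen need and death; the survivors-only version keeps the narrower question visible.

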Dosage and administration	
Active treatment group: 250 µg/vial of sargramostim will be dissolved in 4 mL of physiological saline and 125 µg of which will be administered using inhaler twice daily in approximately 10-15 minutes.
 
Control group: 2 mL of physiological saline will be administered using inhaler twice daily in approximately 10-15 minutes.

Treatment period	5 days, in principle (up to 10 days)
Prohibited concomitant medications/therapies	
【Prohibited concomitant medication】
 
Concomitant use of any unapproved drugs (including off-label use of approved drugs and use at unapproved dosage and administration, excluding steroids as standard treatment at each institution) will be prohibited throughout the study period. In addition, the combination of sargramostim with chemotherapy and radiotherapy is contraindicated. Except treatment/therapy mentioned above, there are no specific prohibited concomitant medications in this study. And steroids used as standard treatment at each institution, approved antiviral agents, or others can be used concomitantly as a part of standard treatment.
 
【Prohibited concomitant therapy】
 
If a subject has started to use invasive ventilation or ECMO, the study drug administration will be terminated after initiation of use of such devices (see "15.1 Study drug discontinuation"). The necessity to use these devices as part of the standard treatment for COVID-19 will be judged based on the subject's condition and medical necessity during the study period.

Study procedures	
COVID-19 patients will be randomly assigned to either of the following two groups in a 2:1 ratio:
 
Sargramostim (125 µg) or physiological saline will be administered by inhalation twice daily for 5 days, in principle (up to 10 days) as Add-on treatment to the standard treatment.
 
(1) Active treatment group (standard treatment plus sargramostim)
 
(2) Control group (standard treatment plus physiological saline)

	Stratified allocation with standard treatment as the allocation factor will be performed for randomization.
Observation period	Period until Day 28 (including the case after discharge)

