Endpoints	
【Efficacy endpoints】
 
Primary endpoint
 
Number of days to achieve at least 2-rank improvement on a 7-point ordinal scale from baseline until Day 28.
 
Secondary endpoints
 
 (1) Changes in alveolar-arterial oxygen partial pressure gradient (A-aDO₂) on Day 5 and at the end of administration from baseline. (2) Number of days until discharge from baseline (days of shifting to Category 7 on a 7-point ordinal scale). (3) Proportion of subjects whose category has shifted to Category 1 or 2 on a 7-point ordinal scale from baseline until Day 28. (4) Changes in pulmonary inflammatory findings on Day 5 and at the end of administration from baseline. (5) Changes in arterial blood-gas parameters (partial pressure of oxygen [PaO₂] and partial pressure of carbon dioxide [PaCO₂]) on Day 5 and at the end of administration from baseline. (6) Changes in inflammatory markers and cytokines at the end of administration from baseline. (7) Distribution and proportion of each category on a 7-point ordinal scale on Day 14 and Day 28. (8) Distribution and proportion of each category of oxygen requirement until Day 14. (9) Other exploratory items (details will be specified separately in the statistical analysis plan). 
【Safety endpoints】
 
Incidence of adverse events and serious adverse event.

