6.3 Rationale for dosage and administration

Dosage and administration of the study drug in this study is based on the fact that the efficacy and safety in Japanese patients with autoimmune pulmonary alveolar proteinosis have been confirmed on the same dosage and administration^{7,9}, and that the efficacy of sargramostim was suggested in the COVID-

19 patients [p=0.053, compared with standard treatment (without sargramostim)] for A-aDO₂, the primary endpoint, in the interim analysis (20/ target number of 80 subjects) of the clinical study being conducted in Belgium¹¹.

Inhalation administration for 5 consecutive days was set based on the fact that inhalation administration for 7 consecutive days has been confirmed safe in the placebo-controlled phase III study in patients with autoimmune pulmonary alveolar proteinosis (investigator-initiated study) conducted in Japan⁷.

In the clinical study¹¹ in COVID-19 patients being conducted in Belgium and the U.S., 5 days was set for inhalation administration of sargramostim. If the investigator determined it necessary to administer sargramostim after the sixth day, sargramostim was to be administered intravenously (approved route of administration in the U.S.) for further five days. Based on this, the administration period in this study was set as "5 days, in principle (up to 10 days)" by the inhalation administration route.

Final observations are to be performed until Day 28 (including the case after discharge from hospital), so that not only the observations during treatment period but also the follow-up observations can be performed to observe prognosis after the end of administration.

Because it is difficult to obtain the placebo preparation of the test drug, an unblinded pharmacist is to prepare the physiological saline for the control group and the control drug is to be administered by inhalation in the same manner as in the active treatment group.

7 Subjects

Patients with moderate-II coronavirus disease-2019 (COVID-19) who were clinically diagnosed pneumonia.

[Rationale]

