  - 1) Period from baseline to the day of discharge will be estimated by treatment group using the Kaplan-Meier method, and comparison between groups will be performed as well using the log-rank test with a significance level of 5%. Definitions of events and censoring are presented in Table 2.3.

2.1.2.10.2.3 Period from baseline to shifting to Category 6 or 7 on a 7-point ordinal scale

- (1) Analysis set : FAS
- (2) Analysis item : period to shifting to Category 6 or 7 on a 7-point ordinal scale from baseline (time point - Day 0)
- (3) Time point : Day 0 to Day 28
- (4) Analytical method :
  - 1) Period from baseline to shifting to Category 6 or 7 on a 7-point ordinal scale will be estimated by treatment group using the Kaplan-Meier method, and comparison between groups will be performed as well using the log-rank test with a significance level of 5%. Definitions of events and censoring are presented in Table 2.3.

2.1.2.10.2.4 Rate of shifting to Category 1 or 2 on a 7-point ordinal scale during the period from baseline to Day 10 or Day 28

(1) Analysis set : FAS

(2) Analysis item : rate of shifting to Category 1 or 2 on a 7-point ordinal scale from baseline (time point - Day 0)

(3) Time point : Day 0 to Day 28

(4) Analytical method :

- 1) The number of patients of whom the category has shifted to Category 1 or 2 on a 7-point ordinal scale and the proportion during the period from baseline to Day 10 or Day 28 will be summarized by treatment group and by time point (number of patients, %).
- 2) The p-values (Fisher's exact test) on Day 10 or Day 28 will be calculated for the rate of shifting to Category 1 or 2 on a 7-point ordinal scale during the period from baseline to Day 10 or Day 28.
- 3) Period from baseline to shifting to Category 1 or 2 on a 7-point ordinal scale will be estimated by treatment group using the Kaplan-Meier method, and comparison between groups will be performed as well using the log-rank test with a significance level of 5%. Definitions of events and censoring are presented in Table 2.3.

2.1.2.10.2.5 Changes from baseline in pulmonary inflammatory findings at each time point

(1) Analysis set : FAS

(2) Analysis item : changes from baseline in pulmonary inflammatory findings (each time point - Day 0)

(3) Time point : Day 0, Day 5, at discontinuation/completion of treatment

(4) Analytical method :

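### Time to Category 1 or 2 is censored at discharge, so its Kaplan-Meier curve reflects in-hospital hazard rather than Day-28 risk, and events after discharge are left undefined

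*SAP*

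**What the plan says.** SAP 2.1.2.10.2.4 analyses worsening to Category 1 or 2, with time points from Day 0 to Day 28, in three items:

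- Item 1 gives the number and percentage of patients who have shifted by Day 10 and by Day 28.
- Item 2 tests those rates: "The p-values (Fisher's exact test) on Day 10 or Day 28 will be calculated for the rate of shifting to Category 1 or 2".
- Item 3 is a time-to-event analysis: "Period from baseline to shifting to Category 1 or 2 on a 7-point ordinal scale will be estimated by treatment group", by Kaplan-Meier, with a log-rank test at 5%. It takes its event and censoring rules from Table 2.3.

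The worsening row of Table 2.3 counts reaching Category 1 or 2 as the event, so death is an event. Patients who complete the study without an event are censored at their last observation. A further line censors "A patient who discontinued or discharged from the hospital", with the time given as "Period until discontinuation or discharge". No reason is stated.

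Protocol secondary endpoint (3) is "Proportion of subjects whose category has shifted to Category 1 or 2 on a 7-point ordinal scale from baseline until Day 28". Note 2 to the schedule in protocol Section 2 says of the scale: "Will be evaluated every day during the period between Day 1 and Day 28". The Synopsis and Section 6.3 extend observation to Day 28 for discharged patients too, and Section 12 has those patients instructed to attend the scheduled observations.

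**The concern.** Kaplan-Meier assumes that a censored patient would have had the same later risk as those still under observation. Discharge is Category 7, the best state on the scale. Censoring there gives recovered patients the risk of those still ill enough to be in hospital, and it sets aside follow-up that the protocol plans to collect.

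Two consequences follow. First, the Kaplan-Meier value is not the Day-28 risk, although nothing in the SAP labels it as in-hospital. The distortion depends on how fast patients leave, so an arm that is discharged sooner can look worse on the curve than in the n (%) of the same section. A lower Day-28 risk that comes from faster discharge can likewise be hidden. Second, Table 2.3 does not say what happens to a patient who reaches Category 1 or 2 after discharge.

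The SAP recognises the mirror image. For the improvement endpoints, Table 2.3 carries patients who discontinued or died to Day 29, and its footnote explains that losing them from the denominator could overstate improvement. Losing discharged patients from the worsening denominator acts in the same way on worsening.

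**Working it through.** **The plan's own figure.** There is none for this endpoint. The one computed design figure, 82.1% power for the primary log-rank test (protocol Section 18), reproduces at 82.7% with continuous times and 83.4% with whole days (4,000 runs). It is not at issue here.

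**Inputs.** From the documents: 40 and 20 patients, two-sided 5%, Day-28 horizon. Borrowed from Section 18 as a stand-in for discharge timing: 10 vs 14 days, SD 4.5. Those figures concern 2-rank improvement, so other values are also shown. Assumed: all worsening rates and event days.

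**Mechanism by hand.** Take 40 patients, with events on Days 2, 6 and 15 and the other 37 discharge days spread as a normal with mean 10 and SD 4.5. The numbers at risk on the event days are 39, 34 and 8.

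- SAP rule: 1 − (38/39)(33/34)(7/8) = 1 − 0.8275 = 17.3%.
- Discharged patients kept at risk: 1 − (39/40)(38/39)(37/38) = 1 − 37/40 = 7.5%, which is the crude 3/40.

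The third event is divided by the 8 patients still in hospital. With events on Days 2, 4 and 6 the SAP rule gives 8.1%, so late events drive the effect.

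**Simulation, equal Day-28 risk.** Discharge days are normal (SD 4.5), rounded and limited to Days 1-27. A worsening patient has an event day uniform over the window and is not discharged first. The true risk is 10% in both arms, and the values are large-sample (400,000 patients per arm).

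| Worsening window | Mean discharge day, active vs control | 1 − KM under the SAP rule |
|---|---|---|
| Days 1-14 | 10 vs 14 | 17% vs 12% |
| Days 1-14 | 12 vs 16 | 14% vs 11% |
| Days 1-14 | 14 vs 18 | 12% vs 10% |
| Days 1-14 | 12 vs 12 | 14% vs 14% |
| Days 1-7 | 10 vs 14 | 11% vs 10% |

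At 40:20 the between-trial SD in the first row is about 10 and 8 points. The SD of the gap is then about √(10² + 8²) = 12.8 points, against a mean gap of about 5.

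**Simulation, equal in-hospital hazard.** With 0.01 per day until discharge and none after (discharge 10 vs 14), the true Day-28 risks are about 9.5% vs 13%. Mean 1 − KM at n = 40 and 20 is about 18% vs 20% (SD about 16 and 18 points). The last observed time is at median Day 19 and Day 22, which fits 1 − 0.99^19 = 17.4% and 1 − 0.99^22 = 19.8%. With discharge capped at Day 27, the large-sample limit is about 1 − 0.99^27 = 23.8%.

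**Log-rank test** (4,000 trials, simulation error about 0.4 points; equal Day-28 risk, Days 1-14, discharge 10 vs 14). Rejection under the SAP rule is about 5% at 10% worsening and about 7% at 20%. With discharged patients kept at risk it is about 3% and 5%.

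**Direction is not guaranteed.** Suppose 5% of discharged patients worsened later. The true risk would be 10% + 0.90 × 5% = 14.5% in both arms. If those events are censored at discharge, the curves stay at 17% vs 12%, too high in one arm and too low in the other.

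**The case against.** The strongest reply is that item 3 is supportive. The protocol endpoint is a proportion, and items 1 and 2 analyse it without discharge censoring. Censoring at a competing event gives a recognised quantity, the in-hospital cause-specific hazard, and the log-rank test is valid for comparing it. No sentence in the SAP says that item 3 estimates Day-28 risk. The sizes above rest on assumed rates, are small against sampling noise, vanish as a gap between arms when discharge is equally fast, and nearly vanish when worsening is early. Much of this stands, and it is why the point is minor. What it leaves open is that the curve is not labelled as in-hospital, sits under a heading and time range that run to Day 28, and gives no reason for dropping planned follow-up.

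Two stronger readings are tempting. One is that the section plainly contradicts itself: a patient discharged on Day 10 and ventilated on Day 20 would be an event in items 1 and 2 but censored on Day 10 in item 3. Table 2.3 does not settle this. Such a patient also fits the event line, and the table sets no precedence between its lines. The classifications conflict only if the censoring line prevails. The other reading would not remove the main problem, because event-free patients still leave the risk set at discharge. The second tempting reading is that the log-rank test is seriously inflated. The calculations do not show that.

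**Conclusion.** The point holds as a minor one. Censoring event-free patients at discharge is informative, so the item 3 curve reflects the hazard in hospital, not Day-28 risk, and need not agree with items 1 and 2. The handling of events after discharge is undefined.

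In the illustrations, a true 10% in both arms appears as anything from 17% vs 12% down to 11% vs 10%. True risks of about 9.5% vs 13% appear as about 18% vs 20%, with so much noise at 40:20 that a single trial would say little. Log-rank rejection is about 5% at 10% worsening and about 7% at 20%, so any inflation is mild at most. All of this depends on worsening and discharge patterns that the documents do not give.

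A reader might infer that the protocol's worsening endpoint, or the trial's main conclusion, is biased. It is not: the n (%), Fisher's test and the primary log-rank test do not use this rule.

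**What to change.** In the worsening row of Table 2.3:

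- keep patients discharged alive at risk to Day 28 or last contact;
- count Category 1 or 2 after discharge as an event;
- censor early only for withdrawal or loss to follow-up;
- apply the same rule to transferred patients. Table 2.3 does not mention transfer, but protocol 15.1 groups it with discharge when listing reasons to stop study drug.

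With complete follow-up, one minus Kaplan-Meier at Day 28 then equals the item 1 proportion.

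If the current rule is kept, state how post-discharge events are classified, label the curve and test as in-hospital hazard, and add a cumulative incidence curve with discharge as a competing event.

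The cost is one or two sentences in the SAP and a change to one derivation, with no new data. The downside is reliance on the post-discharge follow-up already planned: patients lost soon after leaving hospital would still be censored early.
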